11 STATISTICAL CONSIDERATIONS

11.1 Study Outcome Measures

11.1.1 Primary Endpoint

The primary endpoint will be the proportion of subjects who complete >90% of their recommended CMV monitoring tests by 1-year post-transplant. We will use logistic regression modeling to compare this proportion between subjects randomized to DBS testing versus standard office-based testing. Since randomization will be stratified by transplant site and subject's perceived ease of access to blood draw facility, these factors will be used as adjustment factors in the models.

For each subject, the number of CMV monitoring tests performed will be assessed and the percent of recommended tests will be calculated. Subjects with percent completion >90% will be considered a success with regard to the primary endpoint. The personspecific denominator for the proportion, number of expected CMV monitoring tests, will be variable and dependent on subjects' immunosuppression and hospitalizations during the study. For example, subjects in this study that are highly immunosuppressed a weekly monitoring schedule is generally recommended, often throughout the first year after transplantation. If such a subject were discharged from the primary transplant center at day 100, there would be 38 remaining tests until day 365 after HCT (if the subject is still alive at 1 year). We will assess the actual number of tests performed and calculate the percent of tests (e.g. 36/38 = 94.7%). Another scenario would be for a subject that stopped monitoring and was then re-started on high-dose steroids for treatment of GVHD with resumption of weekly testing, resulting in yet another denominator. Study participants in the DBS arm who are hospitalized during the study should not collect DBS samples while admitted. Rather, admitting hospitals should monitor participants for CMV with plasma CMV DNA PCR testing as recommended for their level of immunosuppression. Those inpatient testing timepoints will not be included in the person-specific denominator.

The primary analysis will be an intent-to-treat (ITT) analysis of all subjects randomized. Another key analysis will be the modified intent to treat analysis of all subjects who had at least one test done after discharge from the primary transplant team.

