11.2 Sample Size Considerations

Power calculations utilized a binomial distribution to ascertain the number of subjects needed to detect a clinically meaningful difference in proportions of subjects meeting the primary endpoint ⁴³. Based on our preliminary data, we assumed the proportion of individuals completing >90% of their recommended surveillance tests in the standard office-based testing arm would be in the range of 50-55%. In our previously reported clinical trial, high rates of CMV monitoring completion resulted in the clinically relevant outcome of a low incidence of late CMV disease ²². To be successful, this proof of concept trial needs to demonstrate that similarly high rates of monitoring can be achieved with subject collected DBS monitoring. With 150 subjects, randomized 2:1, we will have 90-96% power to detect an absolute difference in testing rates of 25-30% between subjects in the intervention (80% adherence) and control arms (50% adherence)

DMID/NIAID/NIH CONFIDENTIAL (Table 2). Although the 2:1 randomization does not result in increased statistical power, randomizations that favor the experimental arm (2:1 or 3:1) appear to increase the appeal to the potential study participant and have been used successfully in several recent multicenter CMV randomized trials ^{24,25,44}.

Sample size Total	Sample size DBS group	Sample size Control	Proportion of subjects with >90% Adherence rate DBS arm	Proportion of subjects with >90% Adherence rate Control arm	Sig. level Two- sided	Power
150	100	50	0.8	0.5	0.05	96%
150	100	50	0.8	0.55	0.05	89%
150	100	50	0.8	0.58	0.05	80%

Table 1 Power calculations for primary analysis

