6.3.2. Modified Intention-to-Treat (mITT) Population

The mITT population will include all participants in the ITT who have at least one result for the number of clinician-recommended CMV monitoring tests and remained enrolled through their first scheduled clinician-recommended CMV monitoring test (e.g., a participant assigned weekly clinician-recommended CMV monitoring at discharge must remain enrolled for at least 1 week after discharge to be included in the mITT

population). Participants will be grouped based on the intervention received, where participants that complete at least one self-collected DBS sample will be grouped in the DBS arm and all other participants will be grouped in the SOC arm. This population will be used as a supplemental analysis for all adherence outcome measures.

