	No recommended monitoring schedule available	X	xx	х	XX	х	XX	N/A	N/A
	Withdrew prior to first scheduled clinician recommended CMV monitoring test	X	xx	х	XX	х	XX	N/A	N/A
Completer	Any Reason	х	XX	х	XX	х	XX	х	XX
	Excluded from mITT	х	XX	х	XX	х	XX	n x x x x x x x x x x x x x x x x x x x x x x x x x x x x x x x x x x x x x	XX
	Found ineligible at baseline							х	XX
	No recommended monitoring schedule available		xx	х	XX	X	XX	x	XX
	Withdrew prior to the study close-out visit	х	xx	х	xx	x	xx	x	xx

Table 7: Dates of First Enrollment by Site and Intervention Group

[Implementation Note: If the number of sites and/or groups causes this table to be too wide (wider than the page), then break into 2 tables: one by site and one by treatment group, similar to the demographics tables.

Monthly intervals will be used for the enrollment time.]

		Hutchinso esearch C	on Cancer Center		orial Sloa Cancer (n Kettering Center	Un	iversity of N	linnesota	MD Anderson Cancer Center			All Sites		
Dates of Enrollment	DBS (N=X)	SOC (N=X)	Observati onal (N=X)	DBS (N=X)	SOC (N=X)	Observational (N=X)	DBS (N=X)	SOC (N=X)	Observational (N=X)	DBS (N=X)	SOC (N=X)	Observational (N=X)	DBS (N=X)	SOC (N=X)	Observational (N=X)
Total (Entire period of enrollment)															
May 2019	х	Х	x	х	х	х	х	x	х	х	х	х	x	х	х
June 2019															
N= Number of e	enrolled p	articipant	s.	1	1	1			1	1	1	1		1	1

Inclusion/Exclusion Category	Inclusion/Exclusion Criterion	n ^a	0⁄0 ^b
Inclusion and Exclusion	Number of participants failing any eligibility criterion	Х	100
Inclusion	Any inclusion criterion	Х	XX
	[inclusion criterion 1]	X	XX
	[inclusion criterion 2]	X	XX
	[inclusion criterion 3]	Х	XX
Exclusion	Any exclusion criterion	Х	XX
	[exclusion criterion 1]	X	XX
	[exclusion criterion 2]	Х	XX
	[exclusion criterion 3]	Х	XX
Eligible but not enrolled	Any eligible but not enrolled reason	Х	XX
	[Eligible but not enrolled reason 1]	Х	XX
	[Eligible but not enrolled reason 2]	Х	XX
	[Eligible but not enrolled reason 3]	Х	XX

Table 8: Ineligibility Summary of Screen Failures

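### The protocol's mITT analysis admits only subjects with at least one test done, so it drops certain failures of the adherence endpoint, and the SAP defines a different, ambiguous mITT set

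*Protocol*

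**What the plan says.** Protocol 11.1.1 sets the success rule: "Subjects with percent completion >90% will be considered a success with regard to the primary endpoint". It then fixes the primary population: "The primary analysis will be an intent-to-treat (ITT) analysis of all subjects randomized". The next sentence adds, under the label of a key analysis, the "modified intent to treat analysis of all subjects who had at least one test done after discharge from the primary transplant team".

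SAP 6.3.2 defines mITT differently. Participants must "have at least one result for the number of clinician-recommended CMV monitoring tests" and must have stayed enrolled through their first scheduled test. Its only example is about enrolment: someone on a weekly schedule must remain enrolled for at least a week after discharge. The same section groups participants by intervention received and calls the analysis supplemental.

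SAP Table 6 gives three reasons for exclusion from mITT: exclusion from ITT, "No recommended monitoring schedule available", and withdrawal before the first scheduled test. Having completed no test is not among them, although the table's implementation note says the reasons should agree with the SAP text. SAP section 17, which lists changes to planned analyses, does not mention the mITT definition.

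**The concern.** Someone who stays enrolled with a schedule and does no test has completed 0% and is the clearest failure the endpoint can record. Protocol 15.6 treats missed tests as endpoint data, not as deviations. The protocol's mITT makes entry depend on a post-randomisation event that is part of the outcome, so it deletes exactly these people. It also drops subjects who withdrew or died before a test was due, so not everyone removed is a non-adherer.

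Two things are at stake. The mITT comparison can differ from the ITT comparison for reasons unrelated to the intervention. And a programmer following the protocol sentence would analyse different people from one following SAP Table 6. The mITT feeds SAP Tables 14 to 19, and the Completer population is drawn from it.

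**Working it through.** **Inputs.** From Protocol 11.2: 100 DBS and 50 control subjects, two-sided 0.05, 80% success on DBS, and an assumption that "the proportion of individuals completing >90% of their recommended surveillance tests in the standard office-based testing arm would be in the range of 50-55" percent. Zero-test shares q are not given anywhere. Those below are assumptions.

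**The plan's own figure.** The protocol claims: "With 150 subjects, randomized 2:1, we will have 90-96% power to detect an absolute difference in testing rates of 25-30" percent. With the pooled normal approximation, power = Φ[(Δ − 1.96·√(p̄(1−p̄)(1/100+1/50))) / √(p_D(1−p_D)/100 + p_S(1−p_S)/50)]. For 0.80 vs 0.55, p̄ = (80 + 27.5)/150 = 0.717. The numerator is 0.25 − 1.96 × 0.0781 = 0.097 and the denominator is 0.0809, so power is Φ(1.20) = 88.5%. The three table rows come out at 96.2%, 88.5% and 80.4% against the stated 96%, 89% and 80%. The design figures reproduce.

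**Effect of the rule.** Every zero-tester is an ITT failure, so removal leaves successes unchanged and shrinks the denominator:

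- mITT rate = p/(1 − q), which is at least p in each arm.
- Shift in the difference = p_D·q_D/(1 − q_D) − p_S·q_S/(1 − q_S), which can have either sign.

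For q = 2% DBS and 10% SOC: 0.80/0.98 = 81.6% and 0.55/0.90 = 61.1%. The shift is 1.6 − 6.1 = −4.5 points, so the difference falls from 25.0 to 20.5.

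**Power.** Subjects are scaled by (1 − q) and rounded. The unadjusted Wald log-odds test is enumerated exactly. The planned model also adjusts for site and ease of access.

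| Zero-test share DBS / SOC | mITT rates | Difference (points) | Power |
|---|---|---|---|
| 0 / 0 | 80.0% vs 55.0% | 25.0 | 88% |
| 2% / 10% | 81.6% vs 61.1% | 20.5 | 73% |
| 2% / 20% | 81.6% vs 68.8% | 12.9 | 37% |
| 10% / 2% | 88.9% vs 56.1% | 32.8 | 99% |
| 5% / 2% | 84.2% vs 56.1% | 28.1 | 95% |
| 5% / 0 | 84.2% vs 55.0% | 29.2 | 97% |
| 1% / 4% | 80.8% vs 57.3% | 23.5 | 85% |
| 0 / 4% | 80.0% vs 57.3% | 22.7 | 82% |

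Equal shares do not cancel when there is a real effect: at 5% in both arms the rates are 84.2% vs 57.9%, a difference of 26.3 points.

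**No true effect (55% in both arms).** Without removal the test rejects 4.9% of the time. With 5% DBS and 2% SOC removed (57.9% vs 56.1%) it rejects 5.3%; with 5% and 0, 6.3%; with 10% and 2% (61.1% vs 56.1%), 8.7%.

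In the table rows with shares of 5% or less, the difference moves by at most 4.2 points (29.2 − 25.0). Its standard error in the design is about 8.1 points (the 0.0809 above).

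**The case against.** The strongest reply is that the SAP has largely dealt with this. SAP 3.3.4 and 3.3.5 separate tests expected from tests completed, and the SAP's phrase about a result for the number of recommended tests fits the expected count better. The one-week example and Table 6 support that reading, under which an enrolled zero-tester stays in and fails. SAP Table 5 also reports by arm how many completed at least one recommended test. All of this stands. It leaves a protocol sentence that says something else, a SAP phrase that can be read two ways, and no record of the change.

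Large zero-test shares may also be unlikely: Protocol 2.1 places the start of the drop-off around two months after discharge. That stands too, and is why the larger cases above are only illustrations.

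A reader might infer more than the documents support:

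- **That the trial's main result is at risk.** It is not. The primary analysis is ITT, and SAP 4.5.1 and 6.3.1 count non-completers and early withdrawals as fails.
- **That the SAP also excludes zero-testers.** The wording permits this, but the example and Table 6 point the other way.
- **That only the arm with more zero-testers gains.** Both rates rise. The arms differ in how much.
- **That a large false-positive rate is likely.** With no true effect, removing 20% of DBS and 5% of SOC gives 68.8% vs 57.9% and 23% rejection; removing 30% of DBS gives 67%. Shares that high in DBS would need home-kit users to score zero, which follows from counting only chart-review tests (SAP 3.3.5), combined with the protocol's inclusion rule. Neither document makes that combination: the protocol's DBS arm monitors by weekly home collection, and the SAP's mITT probably keeps zero-testers.

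**Conclusion.** The concern holds for the protocol's definition and for the mismatch with the SAP. The protocol's mITT selects on the numerator of its own endpoint, inflates both arms' success rates, and can understate or overstate the difference. It affects a supporting analysis that the protocol labels key and the SAP labels supplemental. It does not affect the primary inference.

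The size depends on zero-test shares that the documents do not give. With 2% DBS and 10% SOC, power at 80% vs 55% falls from 88% to 73%. With shares of 5% or less the effect is small. The figures assume the design success rates and an unadjusted test. The change is worth making because it costs little and settles which people are analysed.

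**What to change.** In Protocol 11.1.1 and SAP 6.3.2, define mITT as randomised subjects, analysed in the arm assigned, who have a recorded recommended schedule with at least one expected test and were still enrolled on the date of the first expected test, whether or not any test was done. State that zero tests completed counts as a fail. This wording replaces the protocol's condition that a test was done and the SAP's condition about a result.

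The schedule condition has to stay: without an expected test there is no denominator, as for someone recommended no further monitoring from discharge onward. Keep the Table 6 exclusions for no available schedule and for withdrawal before the first scheduled test. Analysing by assigned arm replaces the SAP's grouping by intervention received, which moves a DBS-randomised participant with no self-collected sample into SOC and so also conditions on adherence. Report the number of zero-testers by arm beside the mITT result, and record the change in SAP section 17.

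The cost is a protocol clarification and SAP wording. No new data are needed, because Table 5 already counts by arm those enrolled through the first scheduled test and those who completed at least one. The downside is that success rates in this supporting analysis will look lower than under the protocol's present rule.

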11.1.2 Secondary Endpoint

As a secondary endpoint we will be comparing the incidence of late CMV disease by one year post HCT between the two randomized groups using competing risk regression with death treated as a competing risk event ⁴². Using similar methods, we will also compare the CMV disease incidence of trial participants compared to subjects who received HCTs at the clinical sites in the similar time period but did not participate in the trial. As expected, the planned trial would not be sufficiently powered to detect a difference in late CMV disease incidence from 8% (current standard care) to 2% (observed in clinical trial). A trial powered for that detectable effect size would require 330 subjects to have 80% power (one-sided p values 0.05).

To determine the rate of CMV disease at participating sites during the clinical trial we will collect concurrent retrospective baseline data as well as CMV disease and survival data from subjects that were eligible for randomization but decided not to participate (the majority of subjects return to the transplant center at one year). The purpose of this analysis is to determine whether the subjects who participated in the trial are representative of the population at risk for late CMV disease and whether the phenomenon of late CMV disease continues to occur throughout the study period.

To assess the correlation of CMV viral load between DBS and plasma samples, we will use linear model. Other outcomes will be tabulated and compared between groups using Chi-Square, Fisher's exact, and log rank tests, as appropriate.

The relative contribution of mobile phone reminders, subject adherence to the device, and failures of the testing kit itself will be analyzed among subjects randomized to the DBS arm who did not reach the 90% adherence threshold.

11.2 Sample Size Considerations

Power calculations utilized a binomial distribution to ascertain the number of subjects needed to detect a clinically meaningful difference in proportions of subjects meeting the primary endpoint ⁴³. Based on our preliminary data, we assumed the proportion of individuals completing >90% of their recommended surveillance tests in the standard office-based testing arm would be in the range of 50-55%. In our previously reported clinical trial, high rates of CMV monitoring completion resulted in the clinically relevant outcome of a low incidence of late CMV disease ²². To be successful, this proof of concept trial needs to demonstrate that similarly high rates of monitoring can be achieved with subject collected DBS monitoring. With 150 subjects, randomized 2:1, we will have 90-96% power to detect an absolute difference in testing rates of 25-30% between subjects in the intervention (80% adherence) and control arms (50% adherence)

DMID/NIAID/NIH CONFIDENTIAL (Table 2). Although the 2:1 randomization does not result in increased statistical power, randomizations that favor the experimental arm (2:1 or 3:1) appear to increase the appeal to the potential study participant and have been used successfully in several recent multicenter CMV randomized trials ^{24,25,44}.

Sample size Total	Sample size DBS group	Sample size Control	Proportion of subjects with >90% Adherence rate DBS arm	Proportion of subjects with >90% Adherence rate Control arm	Sig. level Two- sided	Power
150	100	50	0.8	0.5	0.05	96%
150	100	50	0.8	0.55	0.05	89%
150	100	50	0.8	0.58	0.05	80%

Table 1 Power calculations for primary analysis

11.3 Participant Enrollment and Follow-Up

Study is expected to enroll 150 allogeneic HCT recipients who meet inclusion criteria for randomized cohort and 450 allogeneic HCT recipients who meet inclusion criteria for observational cohort over period during which randomization is performed (and one year prior if needed) between four study sites. Follow-up for is described in the time and events schedule in Appendix C.

11.4 Randomization Scheme

Randomization will be done by the SDCC online using the enrollment module of AdvantageEDCSM. Subjects will be stratified at the time of randomization according to transplant site and subject's perceived ease of access to blood draw facility in order to prevent major imbalances within the study.

11.5 Analysis Plan

As described under Primary Endpoint, the primary analysis will be a logistic regression analysis, comparing the study arms in an Intent-to-Treat analysis including all randomized subjects. Prior analyses will include careful checks of all key data elements (primary and secondary endpoints and subject characteristics) to ascertain implausible and missing values. Reports including all missing and implausible values will be generated and elements will be checked with source documents to attempt to correct or replace those values. If a data value is considered to be completely implausible and cannot be corrected with available information, its value will be considered "missing". Once these edits have iterated until no further corrections can be made, each data element will be summarized by study arm, and percent of missing data evaluated. Ideally, missing data will be negligible in this study, but if that is not the case, we will determine the ideal method for handling this to avoid biased results (e.g. inverse probability weighting,

DMID/NIAID/NIH CONFIDENTIAL multiple imputation, etc.). Our final analysis plan will be reviewed prior to data lock and amended as needed before the start of analysis.

The primary study period for subjects that have been withdrawn from the study will be from randomization to the day of withdrawal. A sensitivity analysis will be performed to estimate the impact of withdrawal on the primary endpoint using the maximum possible study period. The study statistician may provide an analysis of aggregate, uncleaned data from the observational cohort on the estimates of late CMV disease and on the sensitivity of CMV detection by PCR in DBS vs plasma samples to the investigators and sponsor for the purpose of abstract preparation or presentation or planning for future studies. While the results provided will not be used to make any decisions about the conduct of this study, they may be used to make decisions on activities external to this trial such as the design of other studies on CMV disease in transplant recipients or on CMV detection methodologies.

11.5.1 Interim Safety Monitoring

Among the first 50 subjects enrolled on the DBS intervention arm and followed for at least a year, if the lower one-sided 90% confidence interval for the percent of subjects experiencing CMV disease by one-year exceeds 8% (operationally 7 out of 50), a DSMB meeting will be convened. The DSMB will be charged with determining whether this exceptionally high rate of CMV disease has plausible clinical explanations related to the subject characteristics, or if it is the result of a failure in the monitoring system, and if so, what the source of the failure is (lack of compliance, failure of the system). Ultimately, they will make a recommendation to the PI as to whether any aspect of the study should be modified or terminated.

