Objectives:	Primary Objective:
	- To evaluate adherence to recommended CMV monitoring duration and interval during the first year after transplant upon enrollment using subject self-collected dried blood spot testing
	Secondary Objectives:
	Evaluate the mean difference between the recommended monitoring that each subject completes between the DBS and the control arm
	Compare the incidence of CMV disease between the DBS monitoring and standard of care arms
	Evaluate the safety of DBS monitoring

Description of Study Design:

This is a randomized clinical trial to assess whether a subject centered, self-collection of DBS samples will improve compliance with the clinical recommendation of weekly CMV testing of HCT recipients who are at high risk for late CMV disease. Subjects will be randomized (2:1) to DBS monitoring or standard of care (per local institution) monitoring. Subjects in the DBS arm will receive training on the collection and shipment of the sample to a central laboratory for CMV PCR testing. Periodic whole blood samples also will be collected along with a DBS sample for plasma CMV PCR testing. Subjects in the standard monitoring arm will be followed per standard of care monitoring for their transplant center. Data from the CMV testing done at the local site will be collected from the subject's chart.

Estimated Time to Complete 18-24 months **Enrollment:**

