9.5 Safety Oversight

9.5.1 Data and Safety Monitoring Board (DSMB)

The DMID DSMB is convened by authority of DMID and is advisory to DMID and the study team. The DMID DSMB must consist of at least three voting members including a biostatistician experienced in statistical methods for clinical trials and a clinician with relevant expertise. Selection of DMID DSMB members should include consideration of clinical trials experience, relevant expertise, prior DSMB service, and absence of significant conflict of interest. DMID is responsible for deciding whether consultancies or the financial interests of the members materially affect their objectivity. Members will notify DMID promptly if a change occurs that may create a potential conflict of interest.

The DMID DSMB will operate under the rules of a DMID-approved charter that will be reviewed and finalized following the organizational meeting of the DSMB. The DMID DSMB Charter serves as the standard operating procedure and defines the primary responsibilities of the DSMB, its membership, the purpose and timing of its meetings, data to be reviewed, and procedures for ensuring confidentiality and proper communication. The following times are the proposed scheduled meetings of the DMID DSMB:

- Organizational DMID DSMB meeting –The first meeting of the DMID DSMB will be primarily organizational and to review the study protocol, safety data shells, and frequency of scheduled meetings. This meeting will occur prior to the initiation of study enrollment.
- Interim analysis data review meeting- Among the first 50 subjects enrolled on the DBS intervention arm and followed for at least a year, if the lower one-sided 90% confidence interval for the percent of subjects experiencing CMV disease by one-year exceeds 8% (operationally 7 out of 50), a DSMB meeting will be convened. The DSMB will be charged with determining whether this exceptionally high rate of CMV disease has plausible clinical explanations related to the subject characteristics, or if it is the result of a failure in the monitoring system, and if so, what the source of the failure is (lack of compliance, failure of the system). Ultimately, they will make a recommendation to the PI as to whether any aspect of the study should be modified or terminated.
- Ad Hoc meeting to review safety events such Unanticipated Problems or SAESIs (breakthrough CMV disease reports).

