6.2. Timing of Analyses

6.2.1. Interim Analyses

The following interim analyses may be conducted prior to the database lock. No additional interim analyses are planned.

- Among the first 50 participants enrolled on the DBS intervention arm, if the lower one-sided 90% confidence interval for the percent of participants experiencing CMV disease by one-year exceeds 8% (operationally 7 out of 50), a DSMB meeting will be convened. The DSMB will be charged with determining whether this exceptionally high rate of CMV disease has plausible clinical explanations related to the participant characteristics, or if it is the result of a failure in the monitoring system, and if so, what the source of the failure is (lack of compliance, failure of the system).
- Additional ad hoc DSMB meetings to review safety events such as UADEs or SAESIs may also be held.

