9.3. Deaths, Serious Adverse Events and other Significant Adverse Events

Proven or probable CMV disease is a serious adverse event of special interest. The number of participants, proportion of participants and Clopper-Pearson Exact 95% confidence interval for all enrolled participants experiencing proven or probable CMV disease between discharge and 365 days after HCT will be

summarized in the randomized groups (Table 22). The same quantities will be summarized between HCT and 365 days after HCT in the randomized groups (Table 23).

To assess whether incidence of possible, probable or proven CMV disease at 1 year differed between intervention groups, the proportional hazards model for the sub distribution of CMV (ShafeFine and Gray, 1999) with death as a competing risk will be fit in the safety population. Example SAS code for this analysis is included below and specifies the EVENTCODE=1 indicate the event of interest is relapse of CMV (status =1), death is the competing risk (status =2), and censored observations are those with Status = 0. The PLOTS =CIF option to obtain cumulative incidence function of each intervention group.

DATA RISK;

TRT=1; OUTPUT;

TRT=2; OUTPUT;

FORMAT TRT TRTGRP;

PROC PHREG DATA=DATA PLOTS (OVERLAY=STRATUM)=CIF;

CLASS TRT (ORDER=INTERNAL REF=FIRST);

MODEL T*STATUS(0)= TRT / EVENTCODE=1;

HAZARDRATIO TRT/DIFF;

```
BASELINE COVARIATES=RISK OUT=OUT1 CIF=_ALL_ / SEED=SEED;
```

RUN;

The outcome of the regression will be the occurrence of possible, probable or proven CMV disease. End of follow-up will be defined as the earliest of death date, date of withdrawal, or 365 days post HCT. Gray's test will be used to test for differences in the sub distribution hazard of CMV disease between intervention groups at the 5% significance level, the cumulative incidence function of CMV diseases presented (Figure 3).

Similarly, for another analysis with all enrolled participants, the proportional hazards model for the sub distribution of CMV disease, with death as a competing risk, will be fit. Gray's test will be used to test for differences in the sub distribution hazard of CMV disease between the All Randomized and Observational groups at the 5% significance level, the cumulative incidence function of CMV diseases presented (Figure 4).

The following listings describing deaths, SAEs, or other significant AEs will be presented:

- Serious Adverse Events of Special Interest (Table 25);

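### The Protocol's numerical CMV-disease trigger waits for a year of follow-up on the first 50 DBS subjects, at about 75–100% of planned enrolment, and the SAP states the rule differently

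*Protocol*

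**What the plan says.** Protocol 9.5.1 and 11.5.1 give the same rule. It applies "Among the first 50 subjects enrolled on the DBS intervention arm and followed for at least a year" and looks at the "lower one-sided 90% confidence interval for the percent of subjects experiencing CMV disease by one-year". If that bound "exceeds 8% (operationally 7 out of 50), a DSMB meeting will be convened". The DSMB then decides whether the excess has a clinical explanation or reflects a failure of monitoring, and recommends whether to modify or stop any part of the study. No interval method is named.

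The SAP repeats the rule in two places, with different scope:

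- SAP 6.2.1: "Among the first 50 participants enrolled on the DBS intervention arm, if the lower one-sided 90% confidence interval" and so on, with no requirement of a year's follow-up.
- SAP 4.1: the same bound and count, with neither the follow-up requirement nor the restriction to the first 50 DBS subjects.

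The Protocol also provides other routes. Section 9.2 has each proven or probable breakthrough case reported within one working day, and sends a cluster, as judged by the medical monitor, to an ad hoc DSMB meeting. Section 9.5.1 lists ad hoc review of these events and lets any party overseeing the trial ask for such a meeting. None of these routes carries a number.

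**The concern.** The trigger exists to find out whether home DBS surveillance is failing to prevent CMV disease. Its value is greatest while subjects are still entering the DBS arm. Read as the Protocol is written, the count is assessed only after the first 50 DBS subjects have completed a year, although proven and probable cases reach the sponsor one at a time and almost at once. If disease were well above the 8% benchmark, the defined review could come when nearly all subjects had already been enrolled.

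The SAP versions could be applied earlier, or to a different group of subjects, so it is unclear which rule governs. The grade of disease is also open. The rule says only CMV disease. The secondary outcome in Protocol 3.2.2 includes possible disease, while expedited reporting in 9.2 covers proven and probable disease only.

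**Working it through.** **1. The stated count.** Lower one-sided 90% bounds with n = 50 and z = 1.2816:

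| Method | 6/50 | 7/50 | 8/50 |
|---|---|---|---|
| Wilson | 7.29% | 8.85% | 10.45% |
| Jeffreys | 7.19% | 8.75% | 10.35% |
| Agresti-Coull | 7.17% | 8.75% | 10.37% |
| Clopper-Pearson | 6.43% | 7.96% | 9.54% |
| Wald | 6.11% | 7.71% | 9.36% |

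Wilson at 7/50: (0.14 + 0.01642 − 1.2816 × √(0.002408 + 0.000164)) / 1.03285 = 0.0885. Clopper-Pearson at 7/50 is the 10th percentile of Beta(7, 44) = 0.0796. The stated 7 therefore reproduces under Wilson, Jeffreys and Agresti-Coull. It also reproduces under mid-P (8.63%), logit (8.81%) and continuity-corrected Wilson (8.06%). It misses under Clopper-Pearson, by 0.04 points, and under Wald.

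**2. When the Protocol's condition is met.** Inputs:

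- 100 of 150 subjects go to DBS (Protocol 5.3.1), so the 50th DBS subject is about the 75th randomised.
- The Protocol Summary gives "Estimated Time to Complete 18-24 months" for enrolment.
- Entry is at day 60–180 after HCT (Protocol 4), leaving 365 − 180 = 185 to 365 − 60 = 305 days, or about 6–10 months, to one year after HCT.
- Assumption: even accrual.

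Formula: month = T/2 + f; share of enrolment = month / T, capped at 100%.

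| Enrolment period T | 50th DBS subject enters | f = 6 months | f = 10 months |
|---|---|---|---|
| 18 months | month 9 | month 15 (83%) | month 19 (100%) |
| 24 months | month 12 | month 18 (75%) | month 22 (92%) |

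The range is 75–100%. If follow-up times are spread evenly between 185 and 305 days, simulation puts the last of the first 50 at about month 18 of 18 or month 21 of 24. About 98–99 or 87–88 of the 100 DBS subjects are then enrolled.

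Sensitivity: if enrolment took 42 of the 54 study months (an assumption, not in the documents), the 50th DBS subject would enter at month 21. Adding 6–12 months (12 if the year runs from enrolment) gives 27/42 to 33/42, or 64–79%.

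**3. Who remains.** In the same simulation, about 43–45 of the later 50 DBS subjects are still in follow-up or not yet enrolled when the condition is met.

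**4. Chance of triggering.** P(X ≥ 7) = 1 − Σ C(50, k) p^k (1 − p)^(50−k), summed over k = 0 to 6:

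| True rate | P(X ≥ 7) |
|---|---|
| 8% | 10.2% |
| 12% | 39% |
| 16% | 71% |
| 20% | 90% |

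The same 50 subjects and the same one-year window are counted whether the meeting is called at the 7th affected subject or at the end. These probabilities therefore do not change with the timing of the call.

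**5. Time gained.** Assume also that events are spread evenly over follow-up and the true rate is 20%. Among simulated trials that reach 7, the 7th affected subject appears on average at about month 10 (18-month enrolment) or month 12 (24-month), with about 55 or 49 DBS subjects enrolled. Waiting means month 18 or 21, with about 99 or 87 enrolled. Calling at the count brings the review 8–9 months forward, with about 40 fewer DBS subjects enrolled (99 − 55 = 44; 87 − 49 = 38).

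**The case against.** The case on the other side is substantial, and it rules out four stronger readings that a reader might infer.

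- *That 7/50 contradicts its own criterion.* SAP 9.3 does call for a "proportion of participants and Clopper-Pearson Exact 95% confidence interval for all enrolled participants", and the matching one-sided 90% exact bound at 7/50 falls just short of 8%. But that interval is a two-sided 95% one for the final tables, not for this rule. The SAP uses Wilson for adherence proportions, and Wilson gives 7. The miss under the exact method is 0.04 points, and a trigger of 7 is more protective than 8.
- *That hardly anyone is left to protect.* Enrolment being nearly complete does not mean follow-up is. About 43–45 later DBS subjects could still benefit.
- *That the year runs from enrolment and so can never be observed.* SAP 4.1 says all participants are followed to 365 days after HCT, and that is the horizon used throughout. One year after HCT is the better reading.
- *That nothing can happen earlier.* Single cases are reported within a working day, ad hoc meetings can be requested by several parties, and false-negative assay results are reportable under Protocol 9.3. The DSMB also reviews its meeting frequency at the organizational meeting, and its charter and report shell are not among the documents reviewed, so earlier scheduled reviews cannot be excluded.

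It is also fair to say that the SAP already omits the wait, so the timing problem belongs to the Protocol text. These points limit the concern but do not remove it. The ad hoc routes rest on judgement, and the one rule with a number is tied in the Protocol to completed follow-up.

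**Conclusion.** The point holds as a matter of timing and consistency. As the Protocol is written, the numerical review falls when about 75–100% of enrolment is complete, given even accrual over 18–24 months and a year counted from HCT; the share is lower if accrual is slower. Calling the meeting when the count is reached keeps the same trigger probabilities and could bring the review forward by several months. The size of that gain depends on the simulation assumptions above.

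The Protocol and the two SAP sections do not state the same rule, and none says which grade of CMV disease counts. The count of 7 stands. The only fault there is that the interval method is unnamed, which leaves the outcome at exactly 7 open to argument.

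**What to change.** Align Protocol 9.5.1 and 11.5.1 with SAP 4.1 and 6.2.1 on one rule:

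- Convene the DSMB as soon as the 7th subject with CMV disease by one year after HCT is identified among the first 50 subjects enrolled on the DBS arm, without waiting for all 50 to reach that point.
- State the rule as this count, in place of the confidence-bound wording, and give its operating characteristics: 10.2% chance of a meeting at a true 8%, 71% at 16%, 90% at 20%.
- Say explicitly whether possible disease counts. If only proven and probable cases count, the running count already exists through one-working-day reporting. If possible cases count, they come from the quarterly chart reviews, and the count will lag accordingly. Restricting the rule to proven and probable disease would make it less sensitive if possible cases are now meant to be included, so this should be an open decision.

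The sponsor's number of 7 is kept and the sample size is unchanged. No new data are needed, since possible disease is already abstracted from charts. The cost is an amendment to the wording of both documents and a DSMB meeting that may be called earlier than now planned.
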